9.1.2 Discontinuation from study

Discontinuation from study is when the participant permanently stops receiving the study treatment, and further protocol-required assessments or follow-up, for any reason.

If a participant is discontinued from the study, an Early End of Treatment visit will be scheduled or performed as soon as possible but within 4 weeks. All assessments planned for the Day 183 visit will be performed except HRCT. If early EOT falls on or after Day 85 visit, HRCT should also be performed (see [Table 8-1](#) for a list of assessments to occur at the End of Treatment visit).

If a participant is unwilling or unable to attend, at the minimum, the End of Treatment visit, and decides to withdraw from the study, the reason for withdrawal will be documented and no further assessments will be obtained.

Please note, if a participant decides to discontinue from the study, a withdrawal of consent should NOT be completed unless the participant meets the particular criteria noted in [Section 9.2](#).

9.1.3 Lost to follow-up

For participants whose status is unclear because they fail to appear for study visits without stating an intention to discontinue from study treatment or discontinue from study or withdraw consent/oppose to the use of their data/biological samples, the investigator must show "due diligence" by documenting in the source documents steps taken to contact the participant, e.g. dates of telephone calls, registered letters, etc. A participant should not be considered as lost to follow-up until this "due diligence" has been completed.

9.2 Withdrawal of informed consent/Opposition to use data/biological samples

Withdrawal of consent/opposition to use of data and/or biological samples occurs in countries where the legal justification to collect and process the data is consent and when a participant meets ALL three criteria:

- Explicitly requests to stop use of their data
and
- No longer wishes to receive study treatment
and
- Does not want any further visits or assessments (including further study-related contacts)

This request should be as per local regulations (e.g. writing) and recorded in the source documentation.

Withdrawal of consent impacts ability to further contact the participant, collect follow-up data (e.g. to respond to data queries) and potentially other country-specific restrictions. It is therefore very important to ensure accurate recording of withdrawal vs. discontinuation based on the protocol definitions of these terms.

In this situation, the Investigator should make a reasonable effort (e.g. telephone, e-mail, letter) to understand the primary reason for the participant's decision to withdraw their consent/exercise data privacy rights and record this information. The Investigator shall clearly document if the participant has withdrawn his/her consent for the use of data in addition to a study discontinuation.

Study treatment must be discontinued, and no further assessments conducted, and the data that would have been collected at subsequent visits will be considered missing.

Further attempts to contact the participant are not allowed unless safety findings require communicating or follow-up.

If the participant agrees, an End of Treatment visit will be scheduled or performed prior to the participant's withdrawal of consent/exercise data privacy rights. All assessments planned for the Day 183 visit will be performed except HRCT. If early EOT falls on or after Day 85 visit, HRCT should also be performed (see [Table 8-1](#) for a list of assessments to occur at the End of Treatment visit).

Further details on withdrawal of consent or the exercise of participants' data privacy rights are included in the corresponding informed consent form.

Novartis will continue to retain and use all research results (data) that have already been collected for the study evaluation, including processing of biological samples that has already started at time of consent withdrawal/opposition. No new Personal Data (including biological samples) will be collected following withdrawal of consent/opposition.

9.3 Study stopping rules

The Sponsor may terminate this study, or a cohort, at any time. The Sponsor will notify investigators if the study is to be placed on hold, completed, or terminated.

Cohort stopping rules

Enrollment in a cohort will be placed on hold if:

- The Sponsor considers that the number and/or severity of AEs, abnormal safety monitoring tests, or abnormal laboratory findings justify putting the cohort on hold

Additionally, the DMC will conduct regular reviews of all safety data in an unblinded format. Following each review, the DMC will provide a recommendation to the Sponsor regarding the appropriateness of continuing the cohort from a safety perspective, as well as any other recommendations relevant to study conduct and/or participant safety.

The DMC may recommend discontinuing the cohort if the event rate in the investigational treated arm is 20% higher compared with placebo. The events include, but may not be limited to:

- cumulative number of deaths and/or;
- number of lung transplantations and/or;
- cumulative number of participants with a confirmed absolute decline of % predicted FVC ≥ 15 from baseline.

The meeting intervals and procedures used to provide and assess the data will be described in detail in the DMC Charter.

9.4 Study completion and post-study treatment

Study completion is defined as when the last participant finishes their End of Study visit and any repeat assessments associated with this visit have been documented and followed-up appropriately by the investigator.

All randomized and/or treated participants will have a safety follow-up visit at least 30 days (see [Section 17](#)) after the last administration of study treatment. The information collected is kept as source documentation. All SAEs reported during this time period must be reported as described in [Section 10.1.3](#).

Continuing care should be provided by the investigator and/or referring physician based on participant availability for follow-up. This care may include:

- Enrollment into another Cohort, if eligible and applicable

9.5 Early study termination by the sponsor

The study can be terminated by Novartis at any time.

Reasons for early study or cohort termination may include but are not limited to:

- Unexpected, significant, or unacceptable safety risk to participants enrolled in the study
- Decision based on recommendations from applicable board(s) after review of safety and efficacy data
- Discontinuation of study drug development

In taking the decision to terminate, Novartis will always consider participant welfare and safety. Should early termination be necessary, participants must be seen as soon as possible for an EOT visit and enter into the safety follow-up period as per their respective cohort. The investigator may be informed of additional procedures to be followed in order to ensure that adequate consideration is given to the protection of the participant's interests. The investigator or sponsor depending on local regulation will be responsible for informing IRBs/IECs of the early termination of the trial.

10 Safety monitoring, reporting and committees

10.1 Definition of adverse events and reporting requirements

10.1.1 Adverse events

An adverse event (AE) is any untoward medical occurrence (e.g. any unfavorable and unintended sign [including abnormal laboratory findings], symptom or disease) in a clinical investigation participant after providing written informed consent for participation in the study. Therefore, an AE may or may not be temporally or causally associated with the use of a medicinal (investigational) product.

The investigator has the responsibility for managing the safety of individual participant and identifying adverse events.

Novartis qualified medical personnel will be readily available to advise on trial related medical questions or problems.

The occurrence of adverse events must be sought by non-directive questioning of the participant at each visit during the study. Adverse events also may be detected when they are volunteered by the participant during or between visits or through physical examination findings, laboratory test findings, or other assessments.

Adverse events must be recorded under the signs, symptoms, or diagnosis associated with them, accompanied by the following information (as far as possible) (if the event is serious refer to [Section 10.1.2](#)):

1. The severity grades
 - mild: usually transient in nature and generally not interfering with normal activities
 - moderate: sufficiently discomforting to interfere with normal activities
 - severe: prevents normal activities
2. The investigator is obligated to assess the relationship between any treatment used in the study (study treatment) and each occurrence of each AE. The investigator will use clinical judgement to determine the relationship. A reasonable possibility of a relationship conveys that there are facts, evidence, and/or arguments to suggest a causal relationship, rather than a relationship cannot be ruled out. Alternative causes, such as underlying disease(s), concomitant therapy, and other risk factors, as well as the temporal relationship of the event to study intervention administration, will be considered and investigated. For causality assessment, the investigator will also consult the IB and/or product information, for marketed products.
The causality assessment is one of the criteria used when determining regulatory reporting requirements.
3. Its duration (start and end dates or ongoing) and the outcome must be reported
4. Whether it constitutes a SAE (see [Section 10.1.2](#) for definition of SAE) and which seriousness criteria have been met
5. Action taken regarding with study treatment.

All adverse events must be treated appropriately. Treatment may include one or more of the following:

- Dose not changed
- Dose Reduced/increased
- Drug interrupted/permanently discontinued

6. Its outcome

Conditions that were already present at the time of informed consent should be recorded in medical history of the participant.

Adverse events (including lab abnormalities that constitute AEs) should be described using a diagnosis whenever possible, rather than individual underlying signs and symptoms.

Adverse event monitoring should be continued for at least 30 days (or 5 half-lives, whichever is longer) following the last dose of study treatment. Details for Safety Follow-up are outlined for each cohort in [Section 17](#).

Once an adverse event is detected, it must be followed until its resolution or until it is judged to be permanent (e.g. continuing at the end of the study), and assessment must be made at

each visit (or more frequently, if necessary) of any changes in severity, the suspected relationship to the interventions required to treat it, and the outcome.

Information about adverse drug reactions for the investigational drug can be found in the Investigator's Brochure (IB).

Abnormal laboratory values or test results constitute adverse events only if they fulfill at least one of the following criteria:

- they induce clinical signs or symptoms
- they are considered clinically significant
- they require therapy

Clinically significant abnormal laboratory values or test results must be identified through a review of values outside of normal ranges/clinically notable ranges, significant changes from baseline or the previous visit, or values which are considered to be non-typical in participant with the underlying disease.

10.1.2 Serious adverse events

An SAE is defined as any adverse event [appearance of (or worsening of any pre-existing)] undesirable sign(s), symptom(s), or medical condition(s) which meets any one of the following criteria:

- fatal
- life-threatening

Life-threatening in the context of a SAE refers to a reaction in which the participant was at risk of death at the time of the reaction; it does not refer to a reaction that hypothetically might have caused death if it were more severe (please refer to the ICH-E2D Guidelines).

- results in persistent or significant disability/incapacity
- constitutes a congenital anomaly/birth defect, fetal death or a congenital abnormality or birth defect
- requires inpatient hospitalization or prolongation of existing hospitalization, unless hospitalization is for:
 - routine treatment or monitoring of the studied indication, not associated with any deterioration in condition
 - elective or pre-planned treatment for a pre-existing condition that is unrelated to the indication under study and has not worsened since signing the informed consent
 - social reasons and respite care in the absence of any deterioration in the participant's general condition
 - treatment on an emergency outpatient basis for an event not fulfilling any of the definitions of a SAE given above and not resulting in hospital admission
- is medically significant, e.g. defined as an event that jeopardizes the participant or may require medical or surgical intervention to prevent one of the outcomes listed above

Medical and scientific judgment should be exercised in deciding whether other situations should be considered serious reactions, such as important medical events that might not be immediately life threatening or result in death or hospitalization but might jeopardize the participant or might require intervention to prevent one of the other outcomes listed above. Such events should be considered as "medically significant." Examples of such events are

intensive treatment in an emergency room or at home for allergic bronchospasm, blood dyscrasias, or convulsions that do not result in hospitalization or development of dependency or abuse (please refer to the ICH-E2D Guidelines).

All new malignant neoplasms will be assessed as serious under “medically significant” if other seriousness criteria are not met and the malignant neoplasm is not a disease progression of the study indication.

All reports of intentional misuse and abuse of the product are also considered serious adverse events irrespective of whether a clinical event has occurred.

Any suspected transmission via a medicinal product of an infectious agent is also considered a serious adverse reaction.

10.1.3 SAE reporting

To ensure participant safety, every SAE, regardless of causality, occurring after the participant has provided informed consent and until the last study visit must be reported to Novartis safety immediately, without undue delay, but under no circumstances later than within 24 hours of obtaining knowledge of the events (Note: If more stringent, local regulations regarding reporting timelines prevail). Detailed instructions regarding the submission process and requirements are to be found in the Investigator folder provided to each site. Information about all SAEs is collected and recorded on the Serious Adverse Event Report Form; all applicable sections of the form must be completed in order to provide a clinically thorough report.

1. SAEs occurring after the participant has provided informed consent until the time the participant is deemed a Screen Failure must be reported to Novartis.
2. Randomized and Treated Participants: SAEs collected between time participant signs ICF until EOS safety follow-up visit.

All follow-up information for the SAE including information on complications, progression of the initial SAE and recurrent episodes must be reported as follow-up to the original episode immediately, without undue delay, but under no circumstances later than within 24 hours of the investigator receiving the follow-up information (Note: If more stringent, local regulations regarding reporting timelines prevail). An SAE occurring at a different time interval or otherwise considered completely unrelated to a previously reported one must be reported separately as a new event.

If the SAE is not previously documented in the Investigator’s Brochure or Package Insert (new occurrence) and is thought to be related to the study treatment, a CMO & PS Department associate may urgently require further information from the Investigator for health authority reporting. Novartis may need to issue an Investigator Notification (IN) to inform all Investigators involved in any study with the same study treatment that this SAE has been reported.

Suspected Unexpected Serious Adverse Reactions (SUSARs) will be collected and reported to the competent authorities and relevant ethics committees in accordance with EU Guidance 2011/C 172/01 or EU Clinical Trial Regulation 536/2014 as per national regulatory requirements in participating countries.

Subjects will be followed for all SAEs until their last study visit. Thereafter, the event should be reported to Novartis Safety only if the investigator considers the SAE to be related to study treatment, unless otherwise specified by local laws/ regulations.

SAEs that are ongoing when the subject completes or discontinues the study will be followed by the investigator until the event has resolved, stabilized, or returned to baseline status. SAE outcome will be recorded on the CRF, as applicable. Only SAEs that are unresolved will continue to be followed by the investigator.

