9.1 Discontinuation from study treatment and from study

9.1.1 Discontinuation from study treatment

Discontinuation of study treatment for a participant occurs when study treatment is permanently stopped for any reason (prior to the planned completion of study drug administration) and can be initiated by either the participant or the investigator.

The investigator must discontinue study treatment for a given participant if he/she believes that continuation would negatively impact the participant's well-being.

Participants who discontinue study treatment must return for an Early End of Treatment visit as soon as possible, but within 4 weeks after discontinuation of treatment. All assessments planned for the Day 183 visit will be performed. HRCT will only be done if discontinuation occurs after Day 85. If the End of Treatment visit occurs in the visit window for the next scheduled visit, then the scheduled visit may serve as the Early End of Treatment visit, and all assessments for the End of Treatment visit should occur at that time. Participants will go on to complete all remaining visits as scheduled, including the Day 183 visit and Safety Follow-up visit (see [Table 8-1](#) for a list of assessments to occur at the End of Treatment and Safety Follow-Up visits). For participants who continue scheduled visits, the HRCT scan will be performed as scheduled at the Day 183 visit.

Discontinuation from study treatment is required under the following circumstances:

- Participant/guardian decision
- The participant becomes pregnant. Study treatment must be discontinued immediately. Report the pregnancy according to instructions in [Section 10.1.4](#)
- If organ transplantation becomes necessary during the study treatment
- The participant is unwilling or unable to comply with the protocol
- Adverse event that puts the participant at risk if continuation on investigational product or in the study, at the discretion of the investigator.
- If a liver or renal event occurs, follow guidelines outlined in [Section 16.1](#) (Appendix 1) and [Section 16.2](#) (Appendix 2), respectively, regarding discontinuation of study treatment.

If discontinuation from study treatment occurs, the investigator should make a reasonable effort to understand the primary reason for the participant's discontinuation from study treatment and record this information.

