17.1.4 Specific Exclusion Criteria

101. Women of child-bearing potential (WOCBP), defined as all women physiologically capable of becoming pregnant, unless they are using highly effective methods of contraception for 3 months prior to screening, during dosing, and until End of Study visit (30 days post last treatment). Highly effective contraception methods include:

- Total abstinence (when this is in line with the preferred and usual lifestyle of the participant. Periodic abstinence (e.g. calendar, ovulation, symptothermal, post-ovulation methods) and withdrawal are not acceptable methods of contraception.
- Bilateral tubal ligation, surgical bilateral oophorectomy with or without hysterectomy, total hysterectomy, or bilateral salpingectomy at least six weeks before taking study treatment. In case of oophorectomy alone, only when the reproductive status of the woman has been confirmed by follow up hormone level assessment is not considered to be of child-bearing potential.
- Male sterilization (at least 6 months prior to screening). For female participants on the study, the vasectomized male partner should be the sole partner for that participant.
- Use of oral, (estrogen and progesterone), injected, or implanted hormonal methods of contraception or placement of an intrauterine device (IUD) or intrauterine system (IUS), or other forms of hormonal contraception that have comparable efficacy (failure rate < 1%), for example hormone vaginal ring or transdermal hormone contraception.

In case of use of oral contraception women should have been stable on the same pill for a minimum of 3 months before taking study treatment.

102. Sexually active males must use a condom during intercourse while taking drug and for 24 hours after stopping study medication and should not father a child in this period. A condom is required to be used also by vasectomized men in order to prevent delivery of

the drug via seminal fluid. In addition, male participants should not donate sperm while taking drug and for 24 hours after stopping study medication.

CCI

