17.1.10 Specific Study Design Considerations

The post-treatment safety follow-up in Cohort 1 will be 30 (+14) days following the last drug administration.

CCI

Table 17-4 LTP001 Specific Safety Assessments

Test Category	Test Name
Thyroid	Triiodothyronine, Free/Total Thyroxine, Thyroid stimulating hormone
Endocrine Function Tests	Aldosterone, Cortisol, Insulin-like growth factor 1, Adrenocorticotropic hormone, Testosterone

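### Deaths and lung transplants before Day 183 can be missed in participants who leave the study, and the end date for SAE collection in early treatment stoppers is worded inconsistently

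*Protocol*

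**What the plan says.** **Participants who leave the study.** Protocol 9.1.2 schedules an early End of Treatment visit within 4 weeks. If the participant will not or cannot attend it and withdraws from the study, "the reason for withdrawal will be documented and no further assessments will be obtained". Section 9.1.3, on loss to follow-up, requires the site to document its attempts at contact and asks for nothing about survival or transplant. Section 9.4 says something different: "All randomized and/or treated participants will have a safety follow-up visit at least 30 days" after the last dose. Section 10.1.3 states that "Subjects will be followed for all SAEs until their last study visit", and that later events are reported only if the investigator considers them related to study treatment. Section 9.2 restricts further contact only after withdrawal of consent, and 9.1.2 says that leaving the study is not to be recorded as withdrawal of consent unless the 9.2 criteria are met.

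**Participants who stop treatment but stay.** Section 9.1.1 says: "Participants will go on to complete all remaining visits as scheduled, including the Day 183 visit and Safety Follow-up visit". Section 17.1.10 says: "The post-treatment safety follow-up in Cohort 1 will be 30 (+14) days following the last drug administration". Section 17.1.4 likewise places the End of Study visit 30 days after the last treatment. Section 10.1.3 gives two end dates for SAEs. Its opening sentence covers every SAE "occurring after the participant has provided informed consent and until the last study visit must be reported to Novartis safety immediately", while its item 2 reads "Randomized and Treated Participants: SAEs collected between time participant signs ICF until EOS safety follow-up visit". Table 8-1 lets exacerbation visits run from Day 1 to EOS.

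**The concern.** Death and lung transplant are two of the four PFS components (Protocol 12.5.1; SAP 2.6.1.1). The cumulative number of deaths and the number of lung transplantations are also events on which the DMC may recommend discontinuing the cohort (Protocol 9.3). Both uses need to know, by arm, who had died or been transplanted by the end of the 26 weeks. If a participant leaves and nobody asks, an unrelated death or a transplant leaves no trace in the data. The effect on a between-arm comparison depends on how many leave each arm, which a trial cannot control.

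The second strand is about dates. If SAE and exacerbation collection ends at a visit timed from the last dose, a site could read the protocol as closing collection while FVC is still being measured up to Day 183.

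**Working it through.** There is no figure in the plan to reproduce on this point, so the check compares passages and the visit calendar.

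**1. Leavers: what is captured up to Day 183**

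- End of Treatment visit missed: nothing further is obtained (9.1.2).
- Lost to follow-up: contact attempts are documented, with no status item (9.1.3).
- New SAE after the last study visit: reportable only if judged related (10.1.3).
- Safety follow-up visit: promised to all randomized and/or treated participants (9.4), which cannot be met alongside 9.1.2. Even if held, it is required only at 30 days or more after the last dose, which need not reach Day 183.

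No other provision for vital or transplant status at Day 183 was found.

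**2. Leavers: what the analysis does with the gap**

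SAP 2.6.1.1 plans Kaplan-Meier estimates for PFS and, if data allow, logistic regression of the event rates for the composite and its components. SAP 2.6.3 is the section for missing values and censoring, and it says only that missing data are not imputed. No PFS censoring rule is given. The plan therefore does not say whether a leaver of unknown status is censored, excluded from the logistic model, or counted as event-free.

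**3. Leavers: how many**

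- Section 17.1.11.1 assumes 15% drop-off, with 47 randomized per group and 40 remaining: 47 − 40 = 7, and 7/47 = 14.9%.
- Table 17-5 uses remaining group sizes of 38, 40 and 43: 47 − 38 = 9 (19.1%) and 47 − 43 = 4 (8.5%).
- One missed event in an arm of 47: 1/47 = 2.1 percentage points of the crude event proportion.

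The 4 to 9 are all planned non-completers. They may include people who stop treatment and stay on visits, and people who attend the End of Treatment visit. The documents give no split, so these counts are a ceiling, under the planning assumptions, on those with unknown status.

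**4. Stoppers who stay: the calendar**

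If the last dose is on Day d, the Cohort 1 safety follow-up falls on Day d + 30 to d + 44.

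| Last dose | Follow-up window | Days before Day 183 | Scheduled visits still to come |
|---|---|---|---|
| Day 29 | 59–73 | 110–124 | 85, 113, 141, 183 |
| Day 57 | 87–101 | 82–96 | 113, 141, 183 |
| Day 85 | 115–129 | 54–68 | 141, 183 |
| Day 113 | 143–157 | 26–40 | 183 |

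The whole window precedes Day 183 when d + 44 < 183, that is, for a last dose on or before Day 138. Its first day does so when d + 30 < 183, that is, up to Day 152.

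**5. Stoppers who stay: does collection actually stop?**

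Item 2 of 10.1.3 and the Table 8-1 exacerbation window, read with 17.1.10, would say yes. Against that stand the opening and closing statements of 10.1.3 (to the last study visit), the 9.1.1 rule that AEs/SAEs are minimum data after treatment stop, and the AE/SAE row of Table 8-1, which covers every visit. A participant still due Day 183 has not had the last study visit on the ordinary meaning of the words. On that reading the uncollected period between follow-up and Day 183 is 0 days.

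**The case against.** **On leavers.** Leaving the study means, by definition, that follow-up stops. The protocol first tries for an End of Treatment visit and requires due diligence before calling anyone lost. It keeps related SAEs reportable, and it follows SAEs that were ongoing at discontinuation until they resolve or stabilize. PFS is a secondary endpoint with 80% intervals in a small study that the SAP calls non-registrational. All of this is fair and limits the number of events at risk. It does not supply status at Day 183 for someone who was well when they left, and it does not remove the contradiction between 9.1.2 and 9.4. A reader might also infer that leavers are the people most likely to die or be transplanted. That is plausible, but nothing in the documents shows it, and the point does not need it.

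**On stoppers who stay.** A reader might infer that months of SAEs go uncollected and attach a percentage of lost events to this. The documents do not support that. Besides the passages in step 5, Section 10.1.1 has AEs sought at each visit, Sections 9.4 and 10.1.1 state 30 days as a minimum, and 9.1.1 names Day 183 before the safety follow-up. SAP 2.1.1 runs the on-treatment period to 30 days after the Day 183 visit when that visit is not missing. Any percentage would need a rate of treatment stoppers who stay and an event rate after stopping, neither of which is given. It would also need zero capture after the follow-up visit, which these passages contradict.

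The wording conflict is left. Item 2 is the specific rule for treated participants, and neither 17.1.10 nor 10.1.3 says where the follow-up falls for someone who stops early and continues. A site that treats the dose-timed End of Study visit as the last visit would then report related SAEs only.

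**Conclusion.** The main point stands. For participants who leave without withdrawing consent, the protocol has no means of learning of deaths or lung transplants up to Day 183, and 9.1.2 contradicts 9.4. Under the planning assumptions this concerns at most about 7 of 47 per arm (4 to 9 across Table 17-5). The number of events missed cannot be estimated from the documents. With arms this small, one or two would be visible in a PFS component (2.1 percentage points each) and in the counts the DMC compares.

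The secondary point is a contradiction in wording. A dose-timed EOS visit falls wholly before Day 183 for a last dose on or before Day 138, while item 2 of 10.1.3 and the exacerbation window end at that visit. Because other passages keep SAE collection open to the last study visit, it shows a risk of inconsistent practice between sites and no certain loss of events.

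**What to change.** 1. In 9.1.2 and 9.1.3, record vital and lung-transplant status at Day 183 for everyone who leaves without withdrawing consent, by telephone or from medical or public records where local rules allow. Reconcile 9.1.2 with 9.4 on whether people who leave have a safety follow-up visit.
2. In item 2 of 10.1.3 and the exacerbation column of Table 8-1, end collection at the later of the Day 183 visit and the safety follow-up visit. Reconcile 9.1.1 with 17.1.10 on when the safety follow-up takes place for early stoppers who continue.
3. The SAP records a decision to terminate the study early. Where collection can no longer be changed, report by arm how many participants have unknown vital and transplant status at Day 183, and state how they are handled in the PFS analyses.

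The cost is one status check for a few participants per arm, plus protocol wording. SAE questions for stoppers who stay are already part of the scheduled visits, so item 2 adds no procedure.
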